**Table 4.b Schedule of Trial Procedures for Subjects Aged 1 to Less Than 4 Years (Cohort 1 for Group 2a; N=120)**

Procedure	Timing	Day 1	Day 3	Day 8	Day 29	Day 32	Day 36	Day 57	Day 134	Day 210 (a)
Visits		X		X	X		X	X		X
Phone Contacts (b)			X			X			X	
Visit Window (days)		-	-1/+2	+3	+3	-1/+2	+3	+3	±7	+7
Signed Informed Consent		X								
Physical Examination (c)		X		(X)	X		(X)	(X)		(X)
Trial Vaccine Administration		X (d)			X (d)					
Diary Card Dispensing		X			X					
Diary Card Delivery				X	X		X	X		
Aes (e)		Day 1-28			Day 28-56					
SAEs (f)		X	X	X	X	X	X	X	X	
Blood Draw for Serology (2 mL) (g)		X			X		X		X	

Use of (X) indicates that samples or procedures that generally will not be performed but may be performed to investigate an AE, previous laboratory abnormality, or at the time of premature discontinuation.

**Footnotes:**

- (a) Day 210 is the 6-month end of study visit.
- (b) Phone contacts are only reminder calls on Days 3 and 32; phone contact on Day 134 is for safety data collection (Protocol Sections 9.3.5 and 9.3.6).
- (c) Complete at the first visit (Day 1), brief physical exam at each vaccination, and symptom-directed thereafter. If a subject early terminates (ET), Day 210 procedures should be performed.
- (d) All subjects receive NoV vaccine at Day 1; subjects in the 1 dose groups in Cohort 1 Group 2a receive a saline placebo injection at Day 29 whereas subjects in the 2 dose groups in Cohort 1 Group 2a receive NoV vaccine at Day 1 and Day 29.
- (e) AEs will be categorized by the investigator by severity (mild, moderate, or severe) and causality (related or not related to vaccine).
- (f) SAEs will be reported to the sponsor within 24 hours of the investigator becoming aware of the event.
- (g) Blood draw for serology at 4 visits (all subjects); 2 mL per time point for a total of 8 mL. Anti-NoV specific GI.1 and GII.4 VLP antibodies by Pan-Ig ELISA and HBGA antibody assays; GMT, GMFR, and seroresponse rate ( $\geq 4$ -fold rise from baseline) will be determined for all available subjects in each formulation group. CCI [REDACTED], and HBGA for a panel of GI.1 and GII.4 strains not represented in the vaccine will not be evaluated for Group 2a subjects. CMI will not be evaluated for Group 2a subjects.

**Table 4.c Schedule of Trial Procedures for Subjects Aged 6 Weeks to Less Than 6 Months (Cohort 2; N=360)**

Procedure	Timing	Day 1	Day 3	Day 8	Day 29	Day 56	Day 59	Day 63	Day 84	Day 112	Day 115	Day 119	Day 140	Day 200	Day 260	Day 293 (a)
Visits		X		X	X			X	X	X		X	X			X
Phone Contacts (b)				X			X				X			X	X	
Visit Window (days)		-	-1/+2	+3	+3	+3	-1/+2	+3	+3	+3	-1/+2	+3	+7	+7	+7	+7
Signed Informed Consent		X														
Physical Examination (c)		X		(X)	(X)	X		(X)	(X)	X		(X)	(X)			(X)
Trial Vaccine Administration		X (d)				X (d)				X (d)						
Diary Card Dispensing		X				X				X						
Diary Card Delivery				X	X			X	X			X	X			
AEs (e)		Day 1- 28				Day 56-84				Day 112- 140						
SAEs (f)		X	X	X	X	X	X	X	X	X	X	X	X	X	X	X
Blood Draw for Serology (2 mL) (g)		X				X			X			X				X

Use of (X) indicates that samples or procedures that generally will not be performed but may be performed to investigate an AE, previous laboratory abnormality, or at the time of premature discontinuation.

**Footnotes:**

- (a) Day 293 is the 6-month end of study visit.
- (b) Phone contacts are only reminder calls on Days 3, 59, and 115; phone contact on Days 200 and 260 are for safety data collection (Protocol Sections 9.3.5 and 9.3.6).
- (c) Complete at the first visit (Day 1), brief physical examination at each vaccination, and symptom-directed thereafter. If a subject early terminates (ET), Day 293 procedures should be performed.
- (d) Investigational study doses will be given at least 28 days before and/or after routine pediatric vaccines given per the national vaccine program. NoV bivalent VLP study doses for the 3 dose groups are given at Days 1, 56, and 112. NoV bivalent VLP vaccine for the 2 dose groups are given at Days 1 and 56 with a saline placebo injection given on Day 112.
- (e) AEs will be categorized by the investigator by severity (mild, moderate, or severe) and causality (related or not related to vaccine).
- (f) SAEs will be reported to the sponsor within 24 hours of the investigator becoming aware of the event.
- (g) Blood draw for serology at 5 visits (all subjects); 2 mL per time point for total of 10 mL. Anti-NoV specific GI.1 and GII.4 VLP antibodies by Pan-Ig ELISA, [CCI](#), and HBGA antibody assays; GMT, GMFR, and seroresponse rate ( $\geq 4$ -fold rise from baseline) will be determined for all available subjects in each formulation group. Serum NoV IgG antibody avidity will be determined pre- and post-vaccination on Days 1, 56, 84, and 140 as available with remaining sera

## 5.0 ANALYSIS ENDPOINTS

Endpoints apply to Cohorts 1 and 2 unless otherwise stated. For subjects in Group 2a, the serologic assays to the vaccine VLPs for the Pan-Ig ELISA and for the HBGA binding assays will each be performed. Notably, the following endpoints will not be performed for Group 2a: Avidity, IgA ELISA, CMI for those aged  $\geq 3$  years, and HBGA binding assay to a panel of GI.1 and GII.4 not represented in the vaccine.

### 5.1 Primary Endpoints

#### *Immunogenicity*

- Seroresponse rate (defined as percentage of subjects with a 4-fold rise or greater) in serum anti-NoV antibody titers for both GI.1 VLP and GII.4 VLP as measured by Pan-Ig ELISA at Day 57 (Cohort 1) and Day 140 (Cohort 2).

#### *Safety*

- Percentage of subjects with solicited local AEs of injection site pain, erythema, induration, and swelling on the day of vaccination and then daily through Day 7 after each vaccination (including the day of vaccination).
- Percentage of subjects with solicited systemic AEs of headache, fatigue, myalgia, arthralgia, vomiting (number per day/intensity), and diarrhea (number per day/consistency) for children aged 4 to  $<9$  years; and irritability/fussiness, drowsiness, loss of appetite, vomiting (number per day/intensity), and diarrhea (number per day/consistency) for children aged 6 weeks to  $<4$  years on the day of vaccination and daily through Day 7 after each vaccination.
- Body temperature on the day of vaccination (approximately 30 minutes and 6 hours later); then daily through Day 7 after each vaccination.
- Percentage of subjects with unsolicited AEs for 28 days after each vaccination.
- Percentage of subjects with SAEs throughout the trial.

### 5.2 Secondary Endpoints

#### *Immunogenicity*

#### Pan-Ig ELISA

- Seroresponse rate in serum anti-NoV GI.1 VLP antibody titers as measured by Pan-Ig ELISA on Day 57 (Cohort 1) and Day 140 (Cohort 2).
- Seroresponse rate in serum anti-NoV GII.4 VLP antibody titers as measured by Pan-Ig ELISA on Day 57 (Cohort 1) and Day 140 (Cohort 2).
- GMT of anti-NoV GI.1 VLP antibody titers as measured by Pan-Ig ELISA on Day 57 (Cohort 1) and Day 140 (Cohort 2).
- GMT of anti-NoV GII.4 VLP antibody titers as measured by Pan-Ig ELISA on Day 57 (Cohort 1) and Day 140 (Cohort 2).

- GMFR of anti-NoV GI.1 VLP antibody titers as measured by Pan-Ig ELISA on Day 57 (Cohort 1) and Day 140 (Cohort 2).
- GMFR of anti-NoV GII.4 VLP antibody titers as measured by Pan-Ig ELISA on Day 57 (Cohort 1) and Day 140 (Cohort 2).

**HBGA Binding Assay**

[figure not shown]
- Seroresponse rate in serum anti-NoV GI.1 VLP and GII.4 VLP antibody titers as measured by HBGA binding assay on Day 57 (Cohort 1) and Day 140 (Cohort 2).
- Seroresponse rate in serum anti-NoV GI.1 VLP antibody titers as measured by HBGA binding assay on Day 57 (Cohort 1) and Day 140 (Cohort 2).
- Seroresponse rate in serum anti-NoV GII.4 VLP antibody titers as measured by HBGA binding assay on Day 57 (Cohort 1) and Day 140 (Cohort 2).
- BT50 of anti-NoV GI.1 VLP antibody titers as measured by HBGA binding assay on Day 57 (Cohort 1) and Day 140 (Cohort 2).
- BT50 of anti-NoV GII.4 VLP antibody titers as measured by HBGA binding assay on Day 57 (Cohort 1) and Day 140 (Cohort 2).
- GMFR of anti-NoV GI.1 VLP antibody titers as measured by HBGA binding assay on Day 57 (Cohort 1) and Day 140 (Cohort 2).
- GMFR of anti-NoV GII.4 VLP antibody titers as measured by HBGA binding assay on Day 57 (Cohort 1) and Day 140 (Cohort 2).

***Safety***

- Percentage of subjects with any AE leading to subject's withdrawal from the trial - from the day of vaccination through Day 210 (Cohort 1) and Day 293 (Cohort 2).

**5.3 Exploratory Endpoints**

CCI

**CONFIDENTIAL**

CCI

## **6.0 DETERMINATION OF SAMPLE SIZE**

This trial is designed to be descriptive and is not based on testing formal null hypotheses, and therefore the sample size was not determined based on formal statistical power calculations. However, for illustrative purposes, the probabilities of detecting 1 or more AEs in this design for various scenarios are provided in Protocol Section 13.3

## 7.0 METHODS OF ANALYSIS AND PRESENTATION

### 7.1 General Considerations

This statistical analysis plan (SAP) is based on protocol Amendment 3, Version 4.0, dated 01 March 2016.

The purpose of this trial is to evaluate the immunogenicity and safety profile of 4 formulations under different dosing regimens in 4 pediatric age ranges. Two cohorts of subjects will be enrolled into the trial (Figure 4.a). Cohort 1 will consist of 4 age groups (4 to <9 years, 1 to <4 years [2 groups] and 6 months to <1 year), enrolled in age-step-down fashion as described in Section 4.4. The youngest age group (Cohort 2, 6 weeks to <6 months) will be the last to complete enrollment. Enrollment into each successive age group is initiated based on DMC recommendation. Hereafter the age groups (5 groups covering 4 age ranges) will be designated as 'group'. The factors under investigation for each group within each cohort include: formulation (4 formulation arms within each group); and number of doses (2 levels for each formulation within each group). For groups 1, 2, 2a, and 3 (in Cohort 1), the number of active doses will be 1 or 2 doses. For group 4 (Cohort 2), the number of active doses will be 2 or 3. Within each cohort, subjects are randomized to 1 of 8 trial arms (2 dose levels for 4 formulations), with group as a stratification factor. The purpose of Group 2a is to evaluate the safety and selected immunogenicity endpoints in subjects in the same age range as Group 2, but who receive the recently manufactured NoV bivalent VLP vaccine. Statistical methods described in the following sections will be essentially the same, but will be done only for the endpoints indicated in Section 5.2.

Immunogenicity and safety endpoints will be summarized descriptively (frequency and percent for categorical data; and number of subjects with non-missing observations, mean [or geometric mean], standard deviation [SD] [or geometric standard deviation {GSD}], median, minimum, and maximum for continuous data, unless specified otherwise) at all relevant study visits, as appropriate. In summary tables for categorical data for which categories are defined on the electronic case report form (eCRF), all categories will be presented as specified, even if the subject count within that category is zero. For other categorical data (eg, AEs and medications), only categories with at least 1 subject will be presented. Unless otherwise specified, for each group summarized, category percentages will be based on the number of subjects in the group with non-missing data and the non-missing 'n' will be displayed for each count/percentage.

Minimum and maximum values will be presented using the same number of decimal places as the recorded data. Means, geometric means, least squares means (LS Means), and medians will be presented to 1 more decimal place than the recorded data. SD and GSD will be presented to 2 more decimal places than the recorded data. The confidence interval (CI) about a parameter estimate will be presented using the same number of decimal places as the parameter estimate (ie, 1 more decimal place than the recorded data). Percentages will be presented to 1 decimal place (eg, 80.3%). All p-values will be rounded to 3 decimal places. If a p-value is less than 0.001, it will be reported as “<0.001”; if a p-value is greater than 0.999, it will be reported as “>0.999”.

In general, summaries and analyses will be provided by formulation/dose combination (the 8 available combinations of the 4 formulations and 2 dose groups), by age group and by cohort. For the by-cohort summaries and analyses, those for Cohort 1 are pooled over the 3 age groups (ie, groups 1 – 3).

Unless otherwise specified, all data collected during the trial will be presented in the subject listings. For all listings where information on screen failure is collected, the screen failures data will be presented at the end of the listing.

All statistical analyses will be generated using SAS Version 9.2 or higher.

#### Handling of Missing Values

There will be no imputation of missing data with the exception of (1) missing or partial dates (ie, start dates of AEs), and (2) titer values measured as below the lower limit of quantification (LloQ) for the particular antigen and assay.

##### *Missing or Partial Dates*

Partial dates will be presented as recorded in the listings. Missing and partial AE start dates will be imputed to determine the relationship between the start date of the event and the dose dates of the double-blind vaccinations.

An adverse event should be temporally associated with the correct vaccination dose as far as possible. If an event has a missing or incomplete onset date, the date will be imputed using the following guidelines. If available date information indicates that the start of an event is between two vaccination dates, then the earliest of the vaccination dates will be used for imputation. For example, if Vaccination 1 is on 01 January 2015 and Vaccination 2 is on 02 March 2015 and the event has an incomplete onset date of February 2015, then the event would have an imputed date of 01 February 2015. If the available start date information is insufficient to distinguish between 1 or more vaccination dates, then the event end date will be used to determine the earliest possible imputed date relative to the latest vaccination. In the above example if an event is known to start in 2015 (day and month missing) and the end date is known as 20 March 2015, then an imputed onset date of 02 March (date of Vaccination 2) will be used. If an event is missing both onset and end date then the last vaccination date will be used as the imputed onset date. Similar logic will be used for partial dates of subjects in age group 4, who receive 3 doses.

The imputation of partial end dates for AEs will consider information such whether the AEs are ongoing by the end of study.

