**Placebo Control:**

Saline will be administered as a single control injection (as the final dose) in order to maintain the trial blind for the 1 dose groups in Groups 1, 2, 2a and 3 (Cohort 1) and for the 2 dose group in Group 4 (Cohort 2). Subjects in the 1 dose groups in Cohort 1 receive NoV vaccine on Day 1 and a saline placebo injection on Day 29. Subjects in the 2 dose group in Cohort 2 receive NoV vaccine on Days 1 and 56 and a saline placebo injection on Day 112.

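### The SAP's rule for partial AE onset dates contradicts its own worked example, and its default for undated events can credit a vaccine event to a saline injection

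*SAP*

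**What the plan says.** SAP 7.1, Missing or Partial Dates, imputes incomplete AE start dates in order to relate each event to the "dose dates of the double-blind vaccinations". Its stated aim is: "An adverse event should be temporally associated with the correct vaccination dose as far as possible". Three rules follow.

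- **Onset known to lie between two vaccinations:** "then the earliest of the vaccination dates will be used for imputation". The example supposes that "if Vaccination 1 is on 01 January 2015 and Vaccination 2 is on 02 March 2015" and that the onset is recorded only as February 2015; "then the event would have an imputed date of 01 February 2015".
- **Start date too incomplete to tell the doses apart:** the end date decides. With the year alone known and an end date of 20 March, "then an imputed onset date of 02 March (date of Vaccination 2) will be used".
- **Neither date available:** "If an event is missing both onset and end date then the last vaccination date will be used as the imputed onset date".

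None of the three treats the saline injection differently from vaccine. SAP 4.4 (Placebo Control) makes saline the final injection in the lower-dose arms. In Cohort 1 the 1-dose arms receive it on Day 29. For the other cohort: "Subjects in the 2 dose group in Cohort 2 receive NoV vaccine on Days 1 and 56 and a saline placebo injection on Day 112".

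The imputed date determines the table cell. SAP 7.11.1 tabulates unsolicited AEs by dose number and in three onset windows: 1-7 days, 8-28 days, and overall to relative day 29. It also gives summaries after any vaccination.

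**The concern.** The first rule and its example do not give the same date. A programmer who codes the sentence and one who codes the example would produce different onset-window tables from the same data. The literal version also overrides information that was recorded: the month is known, and the rule replaces it with an earlier one. Unsolicited AEs in the 28 days after each vaccination are a primary safety endpoint, and an event placed on the day of injection looks like an early reaction.

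The second matter is attribution. When little or nothing is known about the date, the event can fall to the last injection. In half the arms that injection contains no vaccine, so a by-dose table can list under saline an event that followed active vaccine.

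**Working it through.** Relative day = date − vaccination date + 1, as in SAP 7.1 (the dose day is day 1).

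**1. The SAP's example** (dose 1 on 01 January 2015, dose 2 on 02 March 2015, 60 days apart; onset February 2015)

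| Reading | Imputed date | Relative day after dose 1 | Onset window |
|---|---|---|---|
| Sentence taken literally | 01 January | 1 | 1-7 days |
| SAP's example | 01 February | 31 + 1 = 32 | none (past day 29) |

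The sentence does not reproduce the example. The later of (first calendar date compatible with the partial date; date of the vaccination opening the interval) does: max(01 February, 01 January) = 01 February. Both readings attach the event to dose 1. The year-only example (02 March) reproduces under its own rule.

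**2. How often the two readings differ at protocol intervals.** For a month-only onset they differ when a whole calendar month lies between two doses. Day 1 to Day 29 with its +3 window is 28-31 days (Cohort 1). Day 1 to Day 56 with its +3 window is 55-58 days (Cohort 2). I enumerated every first-dose date from 2015 to 2018 (1,461 dates). If dose 1 is on day d of a month of length L, the example's logic gives relative day L − d + 2.

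| Gap (days) | Dose dates where readings differ | Of these, example's date still in days 1-7 | in days 8-29 | past day 29 |
|---|---|---|---|---|
| 28 | 0 (0%) | – | – | – |
| 31 | 27 (1.8%) | 27 | 0 | 0 |
| 55 | 1,179 (81%) | 288 | 891 | 0 |
| 56 | 1,227 (84%) | 288 | 939 | 0 |
| 57 | 1,275 (87%) | 288 | 984 | 3 (0.2% of all dates) |
| 58 | 1,323 (91%) | 288 | 1,028 | 7 (0.5% of all dates) |

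Day 29 is counted with the later window (0, 3, 4 and 20 dates in the last four rows). In Cohort 1 the conflict is nearly absent and never changes the window. In Cohort 2, where the readings differ, about three quarters of dose dates (891/1,179 = 76% to 1,028/1,323 = 78%) see the event move from the later window into days 1-7 under the literal rule.

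The second Cohort 2 interval (Day 56 to Day 112, a +3 window at each end) can run from 53 to 59 days. The readings then differ on 74% to 94% of dates, and at 59 days 27 of 1,461 (1.8%) pass day 29.

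These are shares of possible dose dates, not of events.

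**3. Children whose last injection is saline, by design.** Allocation is equal over 8 arms, 4 of which end with saline.

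- Cohort 1: 480 × 4/8 = 240.
- Cohort 2: 360 × 4/8 = 180.
- Total: 420 of 840 (50%).

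A child who stops before the saline injection has active vaccine as the last one, so 50% is the share as randomized.

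**The case against.** **The wording can be read charitably.** In the first rule the vaccination date may be only the anchor that identifies the dose; the no-dates rule uses different words when it means the onset date itself. The example and the stated aim both fit that reading. This is probably what was intended, but the text does not say so, and the sentence is what will be programmed.

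**A reader might infer that the contradiction decides whether an event counts at all.** The example invites this (day 1 against day 32), but it uses a 60-day gap. At the scheduled first Cohort 2 interval at most 0.5% of dose dates give a result past day 29. Where that happens, leaving the event out of the 28-day tables is correct. SAEs and AEs leading to withdrawal are in any case summarized over the whole study.

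**A reader might also infer that it assigns events to the wrong product.** It does not, because both readings stay with the earlier dose.

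**The strongest temptation is to say that the last-injection default systematically makes the vaccine look safer.** The documents do not support that. The true timing of an undated event is unknown, and it may really have followed the last injection. Saline is there to keep the blind, and SAP 7.11 plans no comparison of vaccine with saline injections. The default is the same in every arm, the assigned arm never changes, and relatedness is assessed separately by the investigator.

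Such events should also be few. The protocol requires start and end dates for each AE, uses 28-day diaries, and runs logic checks for missing data. These points limit the size; they do not remove the possible misattribution in by-dose tables.

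**Conclusion.** The rule is wrong as written: it contradicts its example and, read literally, gives an onset date that the record rules out. The effect is on the day. It is almost confined to month-only onsets in Cohort 2, where it usually moves events between the 1-7 and 8-28 day tables. The number of affected events cannot be derived from the documents.

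The saline point is secondary. By design 420 of 840 children end with saline, so undated events, and year-only events resolved by the end date, can be credited to saline in by-dose tables. It is a possible misattribution of unknown and probably small size, and any-vaccination totals by arm do not move.

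The frequencies assume month-only dates and doses given within the scheduled windows. This is a low-severity correction to make before the analysis is programmed.

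**What to change.** 1. Replace the first rule with: *impute the later of the first calendar date compatible with the recorded partial date and the date of the vaccination opening that interval.* This reproduces the SAP's example. It costs one sentence.
2. The last-injection default may stay. Flag every event whose dose attribution rests on the no-dates rule or on a year-only onset resolved by the end date. After unblinding, add a sensitivity by-dose table that moves those attributed to saline to the last active dose. The cost is one extra table.

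Switching the default to the first injection is not recommended as the remedy. It is no more accurate for an undated event, and it would take events away from later active doses in the arms that receive more than one.

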##### *Titers measured below the LloQ*

If a titer value, for either of the 2 vaccine VLPs or for exploratory endpoint non-vaccine antigens, is measured as below LloQ, it will be imputed as the half of the LloQ in summaries and analyses, but will be listed as reported in the raw serology data. For example, a serologic assay with LloQ = 30 generally reports values below LloQ as “<30”. The data listings will present the values as “<30”, while values of 15 (30/2) are to be used in the summaries and analyses.

Since the missing data resulting from dropouts in vaccine trials are typically classified as missing completely at random (MCAR) [1], a simple way of handling the missing data is to use a

“complete case analysis”. That is, the subjects with missing data are to be excluded. Complete case analysis is essentially being done since the per-protocol analysis set (PPS) excludes subjects not receiving the full vaccine regimen or not having data at the primary endpoint times of Day 57 (Cohort 1) or Day 140 (Cohort 2). If more than 20% of the subjects have missing data for the primary immunogenicity endpoint, multiple imputation methods may be explored as a sensitivity analysis.

